#### **5.8.1.3. Restrictions on Use of Treatments for Underlying Cancer or Bone Metastasis**

Monoclonal antibodies used for the treatment of underlying cancer (eg, bevacizumab (Avastin), trastuzumab (Herceptin), panitumumab (Vectibix)) or bone metastasis (eg, denosumab (Prolia, Xgeva)) are generally permitted if ongoing at stable dose regimen at least 30 days prior to the first day of the Baseline Assessment Period (see [Section 5.8.2.3](#)). However, monoclonal antibody therapies associated with clinically significant peripheral or autonomic neuropathy or joint-related adverse effects or those based on chimeric or murine antibodies (eg, cetuximab (Erbix)) are prohibited within 90 days of the start of the Baseline Assessment Period and during the study until Week 32. Monoclonal antibody therapies which are not specifically listed as permitted (see [Appendix 8](#)) should be discussed with the study clinician on a case-by-case basis.

Small molecule inhibitors (eg, erlotinib (Tarceva), sunitinib (Sutent), lapatinib (Tykerb)) used in the treatment of underlying cancer or bone metastasis are permitted (except for bortezomib) if at a stable dose regimen at least 30 days prior to the first day of the Baseline Assessment Period.

If during the double-blind treatment period prior to Week 8, the subject's underlying cancer or bone metastasis progresses so as to require a new chemotherapy regimen, new concomitant bisphosphonates, new concomitant hormonal anti-cancer treatment, or initiation of radiotherapy to sites of bone metastasis, the subject should be withdrawn from study treatment (eg, due to disease progression) and entered in the Early Termination Follow-Up period (refer to [Section 6.4](#)). Between Week 8 to Week 32, if treatment for underlying cancer

or bone metastasis needs to be initiated or changed (refer to [Section 5.8.2.3](#)), the study clinician should be informed so that guidance may be provided as to whether the subject should be withdrawn from study treatment and entered in the Early Termination Follow-Up period. After the Week 32 visit, standard of care treatment may be prescribed as appropriate, without prior consultation with the study clinician.

#### **5.8.1.4. Other Prohibited Medications**

Herbal, homeopathic, and naturopathic remedies should not be initiated during the study; however, subjects who have taken a stable dose of these products for at least 30 days prior to start of the Baseline Assessment Period will be allowed to continue their regimen.

Cell/gene therapies, investigational therapies, or tumor necrosis factor alpha (TNF- $\alpha$ ) inhibitors (eg, adalimumab, etanercept, infliximab) are generally prohibited and must not be taken within 90 days prior to start of the Baseline Assessment Period or during the study until Week 32. For further guidance, refer to Appendix 8 or contact study monitor or study clinician.

Live attenuated vaccines must not have been taken within 90 days prior to the Baseline Assessment Period and are prohibited during the study. Flumist® Influenza Virus Vaccine Live, Intranasal or other inhaled influenza vaccines (in regions where these vaccines are approved) is the only exception of a live attenuated vaccine that will be permitted during the study.

### **5.8.2. Permitted During the Study**

#### **5.8.2.1. Background Opioid Treatment**

The following oral or transdermal background opioid medications are permitted throughout the study:

buprenorphine	levorphanol	tapentadol
codeine	methadone	tramadol
fentanyl	morphine	
hydrocodone	oxycodone	
hydromorphone	oxymorphone	

Tamper-resistant or opioid abuse-deterrent formulations (which may contain both an opioid agonist and an opioid antagonist) such as the following are permitted, for example:

- Embeda [morphine ER + naltrexone].
- Opana ER [oxymorphone ER with a crush-resistant matrix].
- Remoxy [oxycodone ER in highly viscous liquid gelatin capsule]).

Targin (ie, oxycodone/naloxone for opioid induced constipation) is also permitted.

Background opioids should consist of a fixed regimen of around-the-clock (ATC) opioid(s) plus supplemental “as needed” (rescue) doses of an immediate-release (IR) opioid as determined by the investigator and subject according to accepted clinical guidelines for opioid use. Refer to [Section 6](#) for procedures regarding background opioids during the study.

#### **5.8.2.2. Permitted Non-opioid Analgesics**

Concurrent adjuvant analgesics such as SNRIs, tricyclic antidepressants, anticonvulsant medication, single-agent acetaminophen (paracetamol)  $\leq 3$  grams/day for 3 days or less per week, corticosteroids, or muscle relaxants are allowed provided these drugs were started at least 30 days prior to start of the Baseline Assessment Period and are maintained at a stable dose through Week 8. With the exception of NSAIDs and intra-articular corticosteroids, standard of care analgesia is permitted starting at Week 8 (refer to [Section 5.8.2.5](#) and [6.3](#)). Use of NSAIDs or intra-articular corticosteroids as part of standard of care analgesia is permitted beginning 16 weeks after the last dose of subcutaneous study medication.

Occasional use of acetaminophen (paracetamol) (eg,  $\leq 3$  grams/day for 3 days or less per week) for pain conditions other than cancer pain is permitted.

In certain circumstances, occasional use of usually-prohibited analgesics (eg, NSAIDs) may be permitted. Such circumstances could include outpatient diagnostic procedures (eg, colonoscopy, dental procedures) or limited accidental injury (eg, ankle sprains, minor fractures, minor burns/sunburns). Refer to [Section 5.8.1](#) for limitations and prohibitions on these analgesics. Subjects should also be counseled to avoid scheduling prospective procedures such that pain medications would be needed within 48 hours of a study visit. Limited use of oral, intramuscular or intravenous corticosteroids for non-analgesic purposes such as prophylaxis or treatment of chemotherapy-induced nausea and vomiting is permitted. However, they must not be taken within 48 hours of a study visit where efficacy assessments are being collected. Topical, inhaled and intranasal corticosteroids are permitted. Contact the assigned study monitor or study clinician for guidance/approval regarding the use of prohibited medications for other self-limiting conditions, accidental injury or other surgical procedures as the extent of the condition, injury or procedure and the resulting pain medication usage may require termination from the study.

#### **5.8.2.3. Permitted Concomitant Treatments for Underlying Cancer or Bone Metastasis**

Concomitant anticancer treatment of the subject’s underlying primary cancer or bone metastasis is permitted as follows:

- Concomitant chemotherapy, other than paclitaxel, docetaxel, oxaliplatin, cisplatin, vincristine, thalidomide and bortezomib or those expressly prohibited (see Appendix 8), is allowable provided it was ongoing for at least 30 days before the first day of the Baseline Assessment Period. It is acceptable for the regimen to complete at any time after Randomization.
  - Paclitaxel, docetaxel, oxaliplatin, cisplatin, vincristine, thalidomide and bortezomib are not permitted from 30 days prior to the first day of the Baseline Assessment Period to Week 48.

- A subject with chemotherapy-induced peripheral neuropathy can be enrolled provided the neuropathy has been stable over the 6 months prior to the start of the Baseline Assessment Period and the subject is no longer being treated with a chemotherapy agent associated with peripheral neuropathy.
- Monoclonal antibody therapies used in the treatment of underlying cancer or bone metastasis are allowed (with some exceptions; refer to [Section 5.8.1.3](#)) if part of a stable dose regimen started at least 30 days prior to the first day of the Baseline Assessment Period. It is acceptable for the regimen to complete at any time after Randomization; however, if new treatment is initiated prior to Week 8, the subject should be withdrawn from study treatment. Refer to [Appendix 8](#).
  - Monoclonal antibody therapies associated with clinically significant peripheral or autonomic neuropathy or joint-related adverse effects or those based on chimeric or murine antibodies (eg, cetuximab (Erbix)) are prohibited within 90 days of the start of the Baseline Assessment Period and during the study until Week 32. Refer to [Section 5.8.1.3](#).
- Small molecule inhibitors used in the treatment of underlying cancer or bone metastasis (eg, erlotinib (Tarceva), sunitinib (Sutent)) are permitted (except for bortezomib) during the study if initiated at least 30 days prior to the first day of the Baseline Assessment Period and maintained at stable dose during the double-blind treatment period to at least Week 8.
- Blood and blood products for transfusion are allowed throughout the study.
- Concomitant hormonal anti-cancer treatment (eg, GnRH agonists or antagonists, anti-androgens or anti-estrogens) is allowable if treatment has been ongoing at stable dose for at least 30 days prior to the first day of the Baseline Assessment Period and bone pain still is severe enough to meet inclusion criteria. Post-Baseline, the concomitant hormonal anti-cancer treatment dose regimen should remain stable through at least Week 8.

#### **5.8.2.4. Other Permitted Medications**

Medications for other (non-cancer, non-pain) conditions are permitted. Dose adjustments (includes starting a new therapy) during the study can be made if required, and recorded on the concomitant medication CRF.

Daily low dose aspirin ( $\leq 325$  mg as per local prescribing practice) therapy for cardiovascular prophylaxis is permitted without restriction.

#### **5.8.2.5. Standard of Care Analgesia (after Week 8)**

With the exception of NSAIDs or intra-articular corticosteroids, beginning at Week 8 (or Early Termination Visit 1), the investigator may prescribe standard of care analgesia for subjects intending to complete the 24-week Safety Follow-Up period. In this study, standard of care analgesia refers to treatments approved by FDA (for US subjects) or another

applicable Health Authority (for non-US subjects) to relieve the cancer pain. These medications may include opioids, topical analgesics, capsaicin products and are prescribed at the discretion of the investigator.

Standard of care analgesia may include NSAIDs or intra-articular corticosteroids, but these agents should not be re-instituted on a regular basis until at least 16 weeks have passed since the last dose of study medication (Week 32 or Early Termination Visit 2), in order to ensure tanezumab has been eliminated and to minimize joint safety risk. Standard of care analgesics are not considered study medication but will be reimbursed by Pfizer from Randomization, if allowed per local regulation, while the subject is participating in the study. Cancer or bone metastasis therapies are not reimbursed by Pfizer.

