Protocol Activities	As soon as possible after determining subject will be discontinued from study	Early Termination Visit 1	Early Termination Telephone Contact 1	Early Termination Visit 2	Early Termination Telephone Contact 2	Early Termination Visit 3
		~8 Weeks after last SC dose	~12 Weeks after last SC dose	~16 Weeks after last SC dose	~20 Weeks after last SC dose	~24 Weeks after last SC dose

- a. Subjects discontinuing the study at their request or at the decision of the investigator prior to Week 24 should be withdrawn from treatment and begin the 24-week Early Termination Follow-Up period described in [Section 6.4](#). Subjects who undergo total joint replacement will be followed for 24 weeks after the procedure as described in [Appendix 16](#).
- b. X-rays of major joints (each hip, knee and shoulder) and other at risk major joints identified during the study (see [Section 7.3.9](#)) are to be performed as soon as possible following a decision to withdraw a subject from the study is made, provided at least 30 days have passed since the last set of x-rays were collected. If subject discontinues at a study visit, this may be on the same day the Early Termination 1 visit is conducted.
- c. A serum pregnancy test at Early Termination Visit 3 is not necessary if it was previously obtained at Early Termination Visit 2 (16 weeks after the last SC dose).
- d. Subjects will be asked to continue entering cancer pain scores and opioid treatment weekly until Early Termination Visit 2 which is the visit that occurs after complete washout of tanezumab (5 half-lives), and to enter joint pain scores and NSAID use weekly until Early Termination Visit 3.
- e. Female subjects of childbearing potential are instructed on the contraceptive requirements at Screening and then reminded of these requirements at subsequent visits up to when 16 weeks (at least 112 days) have elapsed after the last dose was administered. Contraceptive requirements are described in [Section 4.4](#).
- f. If needed, opioid regimen may be liberalized, or standard of care treatment (as described in [Section 5.8.2.5](#)) may be initiated, as soon as the site is made aware of the subject's decision to discontinue. NSAIDs or intra-articular corticosteroids should not be re-instituted until at least 16 weeks (112 days) have elapsed since administration of the last dose of study medication.

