### 5.8.1.2. Prohibited Non-opioid Analgesics

The use of analgesics (other than background opioids and permitted uses described in [Sections 5.8.2](#)) is prohibited throughout the study beginning 48 hours (or 5 half-lives, whichever is longer) prior to the start of the Baseline Assessment Period and ending at Week 8.

Use of NSAIDs and COX-2 selective inhibitors, both prescription or over-the-counter (OTC) is prohibited through Week 32 except for occasional use. Management of subjects' NSAID use is described below ([Section 5.8.1.2.1](#)). Intra-articular injection of corticosteroids to any major joint within 30 days prior to the Baseline Assessment Period through Week 32 is prohibited.

Unless the following drugs were started at least 30 days prior to the first day of the Baseline Assessment Period and are maintained at a stable dose, use of concurrent adjuvant analgesics such as single-agent acetaminophen (paracetamol), serotonin norepinephrine reuptake inhibitors (SNRI), tricyclic antidepressants, anticonvulsant medication, corticosteroids, or muscle relaxants is prohibited through Week 8.

Refer to [Appendix 7: Half-Lives of NSAIDs and Other Analgesics](#), for a detailed washout schedule for analgesic medications. Sites must consult product labeling and conduct a taper according to the product instructions if a taper is required.

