## **6.4. Subject Withdrawal/Early Termination**

Subjects may withdraw from the study at any time at their own request, or they may be withdrawn at any time at the discretion of the investigator or sponsor for safety or behavioral reasons, or the inability of the subject to comply with the protocol required schedule of study visits or procedures at a given study site.

If a subject does not return for a scheduled visit, every effort should be made to contact the subject. In any circumstance, every effort should be made to document subject outcome, if

possible. The investigator should inquire about the reason for withdrawal, follow-up with the subject regarding any unresolved adverse events and request that the subject return for follow-up visits as indicated in the schedule below. Subjects of child-bearing potential should be reminded to continue contraceptive measures at least 112 days (16 weeks) after the last dose of study medication.

If the study medication and the allowable background opioid regimen are not providing acceptable pain relief during the double-blind treatment period, the subject should be withdrawn from study treatment (eg, due to lack of efficacy or disease progression per the investigator's judgment) and entered in the Early Termination Follow-Up period.

Subjects discontinuing from treatment (prior to Week 24), either at their request or at the decision of the investigator, will be asked to undergo 24 weeks of post-treatment follow-up (as described in [Section 6.4.1](#)). The 24 weeks of follow-up will be obtained through 3 clinic visits and monthly phone calls to yield 24 weeks of follow-up, as described in [Section 6.4.1](#). In addition, subjects will be asked to continue to enter pain scores for index and non-index cancer pain sites and for major joints via IRT, weekly, until 16 weeks after the subject's last dose of SC study treatment (for cancer pain scores) and through the end of the 24 Week Safety Follow-Up period (for joint pain scores).

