#### Brief summary of procedures for subjects discontinuing from study treatment

X-rays of the knee, shoulder and hip (and any other joint imaged at Screening or identified as at risk during the study) should be performed as soon as possible after the decision to withdraw from the study has been made, provided at least 30 days have passed since the last set of x-rays were collected (refer to [Section 6.4.1](#)).

The remainder of efficacy and safety assessments should be done at the scheduled first visit which is to occur approximately 8 weeks after the last dose of SC study treatment (refer to [Section 6.4.1.1](#), Early Termination Visit 1). The site should also schedule the subject for two additional clinic visits. The second visit should be scheduled to occur approximately 16 weeks after the subject's last dose of SC study treatment (corresponding to more than 5 times the elimination half-life of tanezumab) to collect safety and efficacy data (refer to [Section 6.4.1.3](#), Early Termination Visit 2). Once the clinic visit 16-weeks after the last administration of SC study treatment has been completed and final efficacy assessments have been collected, standard of care analgesia with NSAIDs or intra-articular corticosteroids may be offered to subjects who are completing the remaining 8 weeks of the required follow-up period. The third and final clinic visit should be scheduled to take place approximately 24-weeks after the subject received the last dose of SC study treatment (refer to [Section 6.4.1.4](#), Early Termination Visit 3). Telephone contact will be made with subjects at approximately 12 and 20 weeks following the last SC dose of study treatment. Every effort should be made to have the subject agree to complete the entire 24-week Early Termination Safety Follow-Up described in [Section 6.4.1](#).

Subjects entered in the Early Termination Follow-Up period will be able to take background opioid medication daily up to the Early Termination Follow-Up period Visit 3 (which occurs 24 weeks after the last dose of SC study treatment).

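### For a subject who stops before Week 8, Section 5.8.2.5 and Table 2 note f give different start times for standard-of-care analgesia

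*Protocol*

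**What the plan says.** Section 5.8.2.5 sets the start of standard-of-care analgesia, NSAIDs and intra-articular corticosteroids excepted: "beginning at Week 8 (or Early Termination Visit 1), the investigator may prescribe standard of care analgesia". It lists opioids among these treatments and addresses subjects who mean to complete the safety follow-up.

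The withdrawal procedures in Section 6.4 fix when Early Termination Visit 1 takes place: it is the "first visit which is to occur approximately 8 weeks after the last dose of SC study treatment". The Table 2 column header and the title of Section 6.4.1.1 agree.

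Table 2 note f, attached to the rows on liberalising opioids and on beginning other standard-of-care treatment, refers to Section 5.8.2.5 but says that such treatment "may be initiated, as soon as the site is made aware of" the decision to discontinue.

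Other sections count by study week. Section 5.8.2.2 says "standard of care analgesia is permitted starting at Week 8" and refers to Section 5.8.2.5. The general prohibition in Section 5.8.1.2 runs from a washout "prior to the start of the Baseline Assessment Period and ending at Week 8", with an exception for uses permitted under Section 5.8.2. Week 8 limits without that exception stand in the footnote to Section 5.8.1.1 on opioid-acetaminophen combinations, in the adjuvant-analgesic paragraph of Section 5.8.1.2, and in the opioid and adjuvant-analgesic entries of Appendix 8.

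**The concern.** The subjects caught between the two rules are those whose pain is least controlled. Section 6.4 calls for withdrawal when study medication and the allowed opioids "are not providing acceptable pain relief during the double-blind treatment period". Section 6.2.2.1 directs a subject who needs more than 10% above the baseline opioid dose before Week 8 to leave double-blind treatment. Such a subject has failed on the capped regimen and needs something added.

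A site that works from the concomitant-treatment sections or Appendix 8 finds Week 8 or Early Termination Visit 1 as the start. A site that works from the Early Termination schedule finds an immediate start. The two could manage the same patient differently, and each could point to protocol text in support.

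**Working it through.** The plan states no figure to reproduce. The check compares the two rules for one subject.

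**Inputs**
- Injections on Day 1, Week 8 (Day 57) and Week 16 (Day 113); clinic visits at Week 2 (Day 15) and Week 4 (Day 29), each with a window of 3 days either way (Table 1).
- Early Termination Visit 1 at about 8 weeks, or 56 days, after the last dose (Table 2, Sections 6.4 and 6.4.1.1).

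**Step 1: when Section 5.8.2.5 opens.** A subject who stops before Week 8 has had the Day 1 injection only. Early Termination Visit 1 then falls at about Day 1 + 56 = Day 57, which is also the Week 8 visit day. Both limbs of the sentence therefore give the same date.

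**Step 2: the wait under each rule.** Wait under Section 5.8.2.5, read literally = 57 minus the study day of stopping.

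| Stop at | Section 5.8.2.5, literal | Note f | Early Termination Visit 1 held at the stop |
|---|---|---|---|
| Week 2 (Day 15) | 57 - 15 = 42 days, about 6 weeks | 0 | 0 |
| Week 4 (Day 29) | 57 - 29 = 28 days, about 4 weeks | 0 | 0 |
| After the Week 8 visit | 0, already open | 0 | 0 |

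Moving the stop visit by its 3-day window gives 39 to 45 days and 25 to 31 days. Those ranges keep Early Termination Visit 1 at exactly Day 57, although the protocol places it only approximately, so about 6 and about 4 weeks is as fine as the figures should be read.

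**Step 3: whether the cross-references settle it.** Note f sends the reader to Section 5.8.2.5 for what the treatment is, but that section also fixes a start time, and a different one. Section 5.8.2.2 and the general prohibition in Section 5.8.1.2 defer to Section 5.8.2.5 or to Section 5.8.2 as a whole, so they follow whatever Section 5.8.2.5 says. The limits in Section 5.8.1.1, in the adjuvant-analgesic paragraph of Section 5.8.1.2 and in the two Appendix 8 entries do not defer in this way. Correcting Section 5.8.2.5 alone would leave them standing.

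**Step 4: what is not in conflict.** NSAIDs and intra-articular corticosteroids are held until 16 weeks after the last dose in both places.

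**The case against.** The strongest reply is that the intent is clear. Table 2 is the schedule for early stoppers, Section 6.4.1 sends sites to it, and its two rows are drawn as continuous bars not tied to a visit. Note f is the more specific rule. Section 5.8.2.5 is permissive in form, and it reimburses these analgesics from randomization, which fits poorly with a strict bar before Week 8. This makes note f the likely intention, but the protocol nowhere says that it prevails, and the Week 8 limit recurs in places where a reader would not meet note f.

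The reply also narrows the harm, and that part stands. Subjects in early-termination follow-up "will be able to take background opioid medication daily up to the Early Termination Follow-Up period Visit 3". Note b, on the timing of x-rays, adds: "If subject discontinues at a study visit, this may be on the same day the Early Termination 1 visit is conducted". That contemplates holding the visit at discontinuation, in which case there is no wait. A delay therefore needs a stop before Week 8, a site that overlooks note f, and a first termination visit held on the 8-week schedule.

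A reader might go further and infer that withdrawn patients are left without pain relief. The continuing opioids and note f do not support that. A reader might also infer that analgesia started before Week 8 contaminates the primary endpoint. The documents do not support that either: Section 9.2.1 already imputes missing data from discontinuation before Week 8 according to its reason, and how scores recorded after discontinuation are handled is detail that can properly sit in the SAP.

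**Conclusion.** The contradiction is real and is wrong as written, but it is of low severity and concerns conduct and patient care, not the analysis. For a subject who stops study treatment before Week 8, Section 5.8.2.5 opens standard-of-care analgesia only at Week 8 or Early Termination Visit 1, while Table 2 note f opens it at once.

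The size is a possible delay of up to about 6 weeks for a stop at Week 2 and about 4 weeks for a stop at Week 4. These are maxima under a literal reading, not expected delays. They assume one injection on Day 1, a first termination visit at about 8 weeks, and a site that does not apply note f. I also read note f as covering withdrawals decided by the investigator, since note a to the same table covers both kinds. The protocol does not say how many subjects would stop before Week 8, and no count is estimated here. No bias, power or type I error effect is claimed, and Section 9.2.1 needs no change on this account.

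**What to change.** In Section 5.8.2.5, replace the parenthesis naming Early Termination Visit 1 with: *(or, after earlier discontinuation of study treatment, as soon as the site is aware of the decision to discontinue)*. Keep the 16-week restriction on NSAIDs and intra-articular corticosteroids as it is.

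Add the same clause, or a cross-reference to Section 5.8.2.5, to the Week 8 limits in:
- the Section 5.8.1.1 footnote on opioid-acetaminophen combinations;
- the adjuvant-analgesic paragraph of Section 5.8.1.2;
- the opioid and adjuvant-analgesic entries of Appendix 8.

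Section 5.8.2.2 and the general prohibition in Section 5.8.1.2 need no edit of their own. The cost is one replaced parenthesis and a few short insertions at the next amendment, with no new data, visits or analyses.
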